## 8.1.3 Device Deficiency (DD)

A DD is an inadequacy of a medical device with respect to its identity, quality, durability, reliability, safety or performance. DD include malfunctions, use errors and inadequate labeling.

DDs that did not lead to an AE/SAE but could have led to an SAE if:

- suitable action had not been taken, or
- intervention had not been made, or
- circumstances had been less fortunate.

(DDs with SADE potential) are reported as specified for serious adverse events (SAEs/SADEs) in Section 8.3.1. Device Deficiencies will be classified into:

- DDs with Serious Adverse Device Effect (SADE) potential
- DDs without SADE potential

Device Deficiencies will be collected as described in Section 7.3.13. DDs that lead to an AE/SAE will be recorded on the adverse event form as well.

# 8.1.4 Adverse Device Effect (ADE)

An ADE is an AE related to the use of an investigational medical device. This definition includes AEs resulting from insufficient or inadequate instruction for use, deployment, implantation, installation, or operation, or any malfunction of the investigational medical device. This definition includes any event resulting from use error or from intentional misuse of the investigational medical device. Any AE which has even a possible relationship to the investigational device will be classified as an ADE.

### 8.1.5 Serious Adverse Device Effect (SADE)

A SADE is an adverse device effect that has resulted in any of the consequences characteristic of a serious adverse event (see Section 8.1.2).

#### 8.1.6 Unanticipated Serious Adverse Device Effect (USADE)

An USADE is a SADE which by its nature, incidence, severity or outcome has not been identified in the current version of the Risk Management Report (35), IfU (Annex 1, Annex 2) or Table 5 in the current protocol. The term "unexpected" is considered as equivalent to "unanticipated".

## 8.1.7 Anticipated Serious Adverse Device Effect (ASADE)

An ASADE is an SADE which by its nature, incidence, severity or outcome has been identified in the Risk Management Report (35) or IfU (Annex 1, Annex 2). The term "expected" is considered as equivalent to "anticipated". For a compiled list of expected events see Table 5 "Listing of expected AE's and ADE's".

#### 8.2 Assessment of Adverse Events and Device Deficiencies

Each AE should be assessed by the Investigator or another suitably qualified clinician who is trained in recording and reporting AEs and has been delegated to this role (such delegation must be captured in the Site Signature and Delegation of Authority Log) for seriousness, relationship to the investigational device or the procedure and severity as described in this chapter. A rationale shall be provided (short narrative) for each assessment.

Sponsor will review the investigator's assessment of:

- all adverse events and determine and document in writing their seriousness and relationship to the investigational device and procedure
- all device deficiencies and determine and document in writing whether they could have led to a serious adverse device effect

In case of disagreement between the sponsor and the principal investigator(s), both opinions will be communicated to concerned parties. The sponsor will evaluate the AEs for expectedness as described in Section 8.2.7

## 8.2.1 Seriousness

An AE will be described as serious if it meets the definition in Section 8.1.2.

# 8.2.2 Relationship to the investigational device

The Investigator should assess the relationship of the AE to the investigational device. In this study only the study implants (study control and study test implant) need to fulfil the protocol requirements, thus the relationship will be assessed to the study implant (=investigational device). Consequently, **AE's at implant positions of study implants** need to be assessed for relationship to the investigational device (study implant).

The relationship should be assessed using the following categories:

• Related – there is a reasonable causal and temporal relationship between the treatment with the investigational device and the AE.

- Possibly related or unknown The relationship between the treatment with the
  investigational device and the adverse event is less likely; however, the determination that
  there is no relationship cannot be made or is unknown.
- Not related no relationship between treatment with the investigational device and the AE is obvious.

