# 3.3 Study Treatment

Patients will receive Straumann® Bone Level Tapered (BLT), Roxolid® implants with a SLActive® surface (test device) and a SLA® surface (control device) within the intended use (see IfU in Annex 1, Annex 2). Based on randomization (0), two different quadrants will be assigned for either control or test implant placement (study test and study control quadrant). Indications sites are premolars, molars and canines in mandible and maxilla and extraction need to have been performed more than 3 months ago (healed extraction sites). Implants will be 8, 10, 12 or 14 mm of length and with a diameter of 3.3 or 4.1 mm. Particular care should be used when placing small-diameter implants (diameter 3.3 mm) in the molar region.

Per patient, one control and one test implant will be appointed as study control and study test implant ("study implants"). An implant (test or control device) qualifies as study implant if the implant is assessed as primary stable (as defined in Section 7.2.3), the abutment torque is at least 15 Ncm at surgery and the implant site fulfills the eligibility criteria (canine to molar, extraction/ tooth loss more than 3 months ago, soft tissue grafting procedures more than 3 months and bone grafting procedures more than 6 months ago). If there are several control or test implants placed in a study quadrant which qualify as study implant, the most mesial implant satisfying all the criteria, will be appointed as study implant.

Screw retained abutments (SRA) of 2.5mm height will be placed at the same time as the implants and covered with a healing/ protective cap. The implants will be restored with a single crown or splinted restorations 10 weeks after implant placement (implant loading).

Further details can be found under 7.2 (treatment procedures)

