**Note**: if there is no control and test implant available (one of each) that qualify as study implants (implant is assessed as primary stable (as defined in Section 7.2.3) at surgery, the abutment torque is at least 15 Ncm at surgery and the implant site fulfills the eligibility criteria, see Section 3.3 for further details), in 2 different quadrants, the patient needs to be **withdrawn** (see section 3.7.3). If primary stability of any implant not given this needs to be reported as ADE.

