## 7.3.8 Implant Survival

Implant survival will be defined as follows:

A surviving implant is defined as an implant in place at the time of the follow-up. Any implant loss shall be assessed as an early loss (implant fails before being osseointegrated) or late loss (after being osseointegrated).

The basis for implant survival analysis are the study control and study test implants within the ITT population. Implant losses of the other implants will be recorded as AE's.

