## Mechanical complications may be:

- Loss of retention
- Fracture and/or chipping
- Fracture of framework
- Loosening of occlusal screw
- Fracture of occlusal screw
- Loosening of abutment

A failure is defined as an event leading to: the loss of the reconstruction.

Complications and failure of prostheses from all implants placed at surgery will be recorded under the normal AE reporting (see also mechanical complications listed as potential expected Adverse Events and Adverse Device Effect in Table 5).

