**Table 4: Summary of the Classification for Adverse Events** 

Adverse events	Non-device related	Device or procedure related		
Non- serious	Adverse Event (AE)	Adverse Device Effect (42)		
Serious	Serious Adverse Event (SAE)	Serious Adverse Device Effect (SADE)		
		Anticipated	Unanticipated	
		Anticipated Serious Adverse Device Effect (ASADE)	Unanticipated Serious Adverse Device Effect (USADE)	

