# 8.2.3 Relationship to the Procedure

The Investigator should assess the relationship of the AE to the procedure (dental implant treatment, which involves implant placement and prosthetic restoration). In this study, this mean any procedure related to **dental study implant treatment**. The relationship should be assessed using the categories described in Section 8.2.2.

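### The ADE table behind the safety co-primary mixes two scopes (nominated study implants only, and any implant), and new adverse events are not clearly collected in implanted patients withdrawn at surgery

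*Combined protocol and SAP*

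**What the plan says.** **Relatedness.** Section 8.2.2 equates the investigational device with the nominated implants, "thus the relationship will be assessed to the study implant (=investigational device", and asks for relatedness of AEs at study implant positions. Its reason is that only these implants have to meet the protocol's requirements. Section 8.1.4 derives ADE status from that relationship: "Any AE which has even a possible relationship to the investigational device will be classified as an ADE". The column heading in Table 4 is wider, "Device or procedure related", but 8.2.3 restricts the procedure to study implant treatment ("In this study, this mean any procedure related to").

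**Nomination.** Under 3.3 one test and one control implant are nominated per patient. Each must be primary stable, have an abutment torque of at least 15 Ncm at surgery and lie in an eligible site. Where several qualify, "the most mesial implant satisfying all the criteria, will be appointed as study implant".

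**Other implants.** Section 7.3.8 states: "Implant losses of the other implants will be recorded as AE's". On prostheses, 7.3.9 states: "Complications and failure of prostheses from all implants placed at surgery will be recorded under the normal AE reporting". The Note in 7.2.3 states: "If primary stability of any implant not given this needs to be reported as ADE".

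**Use.** ADEs, with device deficiencies that had SADE potential, form the safety primary endpoint (3.4.1). Section 9.2 answers the safety hypothesis with descriptive ADE listings and tables by treatment, severity, relatedness and outcome.

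**Withdrawal.** A patient without one qualifying implant of each type in two quadrants must be withdrawn (3.7.3). AE collection stops at withdrawal or at the final visit (7.3.12). The safety population is every enrolled subject who received a BLT Roxolid implant (9.3).

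**The concern.** The safety claim is about the SLActive surface, and the ADE table is half of the evidence for it. That table is neither a count for the nominated implants, because the 7.2.3 Note brings in others, nor a count for all implants of each surface, because later events at the others are left out. A reader comparing the surfaces cannot tell which implants are at risk of contributing a row, or what the denominator is.

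The label carries further. A SADE is by definition an ADE (8.1.5), so a serious later event at a non-nominated implant would be an SAE but could not be a SADE, ASADE or USADE. Section 9.2 also promises a summary of relatedness for individual AEs, while 8.2.2 requires no such assessment at non-study positions.

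For patients withdrawn at surgery the stake is the data themselves. These patients count in the safety population, and low stability or torque may be the reason they left. New events in them have no stated collection procedure.

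**Working it through.** **1. Is there a figure to reproduce?** Not for this point. The safety co-primary has no rate, threshold or sample size. The plan's only power figure, 92.4% in 9.4, belongs to bone level. With SD of the difference √(0.20² + 0.22²) = 0.2973 mm, distance to the margin 0.10 + 0.03 = 0.13 mm, 51 pairs and one-sided alpha 0.05, the noncentral t gives 92.44%. It agrees, and nothing below depends on it.

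**2. Following an event through the definitions.**

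| Event | Nominated study implant | Other BLT implant |
|---|---|---|
| Lack of primary stability at surgery | Cannot occur: stability is a condition of nomination (3.3) | ADE (Note in 7.2.3) |
| Later implant loss | ADE if at least possibly related (8.1.4, 8.2.2) | AE; not assessed against its own device or procedure (8.2.2, 8.2.3) |
| Device deficiency | Recorded (7.3.13) | Recorded (7.3.13) |

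Every ADE that the Note requires therefore concerns an implant that 8.2.2 does not count as the investigational device. A non-nominated implant that is unstable at surgery gives an ADE; if it stays in place and is lost later, that loss is only an AE.

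**3. Does another section close the gap?** Section 8.2 has the sponsor review relatedness of all AEs, but to the investigational device, the term that 8.2.2 has already narrowed. Section 7.2.3 allows complications at any BLT implant placed to be reported as AE or ADE, but only in the surgical documentation. Later events remain outside.

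**4. Size of part (a).** Implants with relatedness assessment: 2 × 60 = 120, if all 60 planned patients contribute a pair. The documents do not give the number placed. If m is the mean number of SLActive implants per patient (an assumption), the share outside assessment is 1 − 1/m: 0% at m = 1, 1 − 1/1.5 = 33% at m = 1.5, and 1 − 1/2 = 50% at m = 2. This is a share of implants, not of events.

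**5. Size of part (b).** Planned follow-up after placement is 10 weeks to loading plus 12 months (Table 3): 10 + 365.25/7 = 10 + 52.2 = 62.2 weeks. The windows are ±10 days at Visit 7 (10/7 = 1.43 weeks) and ±3 weeks at Visit 9. So 62.2 ± 4.43 gives 57.7 to 66.6 weeks. Under 7.3.12, new AEs are collected for none of these weeks in a patient withdrawn at surgery. The number of such patients is not stated; the 20% dropout allowance in 9.4 is not split by cause.

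**6. The competing text for part (b).** Sections 3.7.3 and 11.3.1 say patients will be advised to attend follow-up visits, safety data being one purpose. In context both address patients who choose to leave, and neither sets visits, a form or a duration. Section 8.4 follows events already open; it does not provide for finding new ones.

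**The case against.** The strongest reply is that 8.2.2 is a reasoned choice. Other implants may stand in recently extracted or grafted sites that 3.3 bars for study implants, and attribution there is harder. That stands as a reason for a separate study-implant table. It does not explain the 7.2.3 Note.

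The Note can be read as a deliberate exception, since under 8.2.2 alone primary instability could never be an ADE. That is plausible, and because AEs carry the implant position (7.3.12) these rows could be separated. The plan neither states the exception nor says that the table will be split.

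A reader might infer that events at the other implants vanish. They do not: they are collected with position (7.3.12), reviewed for expectedness (8.2.7) and summarized by treatment as AEs (9.2), and deficiencies cover all sponsor products (7.3.13). Nor do 7.3.8 and 7.3.9 exclude ADE status by themselves. AE is the umbrella term (8.1.1), so they name a reporting route; the exclusion comes from 8.2.2 and 8.2.3. One might also infer that a splint with a study implant brings a neighbouring implant's event into scope, but 7.2.4 only asks for the splint to be documented.

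Finally, the co-primary is descriptive, so the practical consequence is limited. That also stands.

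**Conclusion.** Both parts hold in a limited form and should be corrected.

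(a) The ADE table for the safety co-primary mixes two scopes. What is lost for later events at non-nominated implants is ADE classification, not data. Size and direction cannot be derived, and the effect is nil if every patient receives exactly two implants and both qualify. With no test or threshold for safety, the documents do not support a claim of a biased test.

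(b) Implanted patients withdrawn at surgery belong to the safety population, but the operative rule stops collection of new AEs with about 62 planned weeks still to run. It would be too strong to say that the plan intends no safety follow-up for them: 3.7.3 and 11.3.1 point the other way but give no procedure. The number affected is unknown.

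**What to change.** 1. Reconcile the Note in 7.2.3 with 8.2.2 and 8.2.3 so that ADEs have one stated scope, preferably by recording device and procedure relatedness for AEs at every BLT position placed at Visit 2. Cost: protocol wording and one relatedness field on AEs that already carry the position.
2. In 9.2, show ADEs for the nominated study implants and, in a separate table, for the other BLT implants by surface with implants placed as the denominator. Keep the two randomized quadrants apart from any others: 7.2.1 randomizes only two, and its wording (figure aside) does not say which surface goes elsewhere, so a pooled comparison could mix randomized with non-randomized sites. Downside: attribution is harder at sites that need not meet the eligibility criteria; the study-implant table keeps the sponsor's intended view.
3. Reconcile 7.3.12 with 3.7.3, 11.3.1 and the safety population in 9.3 so that AE collection continues, subject to consent, for implanted patients withdrawn at surgery, with contacts and duration stated. Cost: a few extra contacts.

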# 8.2.3 Relationship to the Procedure

The Investigator should assess the relationship of the AE to the procedure (dental implant treatment, which involves implant placement and prosthetic restoration). In this study, this mean any procedure related to **dental study implant treatment**. The relationship should be assessed using the categories described in Section 8.2.2.

## 8.2.4 Severity

Each AE should be assessed by the Investigator for its severity, or the intensity of an event experienced by a patient, using the following:

- Mild discomfort noticed, but no disruption in daily activities;
- Moderate discomfort sufficient enough to reduce or affect normal daily activity.
- Severe inability to work or perform normal daily activity.

The term "severe" used to describe the intensity of an event should not be confused with the term "serious", as defined in Section 8.1.2.

#### 8.2.5 Outcome

The outcome should reflect the status of the adverse event at the moment of recording.

- **Resolved** The subject fully recovered from the event without any sequelae. This option also applies when it is unknown whether there are sequelae.
- Resolved with sequelae The subject's condition stabilized despite the persistence of sequelae (e.g., lesion or medical condition which is a consequence of the event). This option does not apply to irreversible congenital anomalies (see under "ongoing").
- Ongoing The subject has not yet recovered from the event. By convention, in the case of
  an irreversible congenital anomaly, the "Ongoing" option should be chosen and understood
  as "Not recovered/Not resolved". The same applies to conditions that are not yet resolved,
  but are controlled by medication (e.g., diabetes, epilepsy) and therefore may not have any
  symptoms.
- Worsened The severity of the AE/ADE increased.

- Fatal The event is related to a death; whether it caused death or contributed to it. If the subject died of a different cause, prior to resolution of the AE/ADE, the outcome of this AE/ADE should designated "Ongoing", and not "Fatal", and an end date should not be specified.
- Unknown: Knowledge of the current status of the AE/ADE is truly not available to the Investigator (i.e. event was ongoing at last observation, but no further contact with the subject could be established). However, all efforts should be made to determine the outcome of any ADE, especially that of an SAE/SADE.

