# 3.4 Endpoints

#### 3.4.1 Primary Endpoint

The following parameter will be measured as primary endpoint:

- Bone level change 12 months after implant loading.
- Occurrence of adverse device effects and device deficiencies that could have led to a serious adverse device effect

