## Safety and tolerability analysis

The safety analysis will be performed on data collected as specified under 7.3.12 and 7.3.13

The analysis of safety assessments in this study will include summaries of the following of safety and tolerability data collected for each subject:

- Adverse events
- Serious adverse events
- Adverse device effects
- Device deficiencies
- Device deficiencies that could have led to a serious adverse device effect

Summaries of the incidence rates (frequencies and percentages), severity, outcome and relationship to the investigational device and or/ study procedures of individual AEs will be

prepared. AEs which concern an implant position where a BLT, Roxolid® implant was placed during surgery or AEs which are related to a treatment procedure at such a position will be summarized by study treatment and overall and the used products at this position will be listed.

DDs will be summarized per medical device type (implant type, abutment type, instruments).

To address the co-primary objective of this study "SLActive® implants are safe" a descriptive assessment of adverse device effects and device deficiencies that could have led to a serious adverse device effect will be made, this will include listings and tables by treatment, severity, relatedness and outcomes.

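### The adverse event outcome code *Resolved* also takes in events whose sequelae status is unknown, so the safety outcome tables can overstate confirmed complete recovery

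*Combined protocol and SAP*

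**What the plan says.** Section 8.2.5 (Outcome) lists the codes for the status of an adverse event. Three matter here.

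- *Resolved*: "The subject fully recovered from the event without any sequelae". The next sentence widens it: "This option also applies when it is unknown whether there are sequelae".
- *Resolved with sequelae*: "The subject's condition stabilized despite the persistence of sequelae".
- *Unknown*: "Knowledge of the current status of the AE/ADE is truly not available to the Investigator". The example given is an event still ongoing when last seen, with contact then lost. This entry also says that "all efforts should be made to determine the outcome of any ADE, especially that of an SAE/SADE".

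Section 3.4.1 gives the safety part of the primary endpoint as "Occurrence of adverse device effects and device deficiencies that could have led to a serious adverse device effect". In section 9.2, under the safety and tolerability analysis, the hypothesis that SLActive implants are safe is addressed as follows: "a descriptive assessment of adverse device effects and device deficiencies that could have led to a serious adverse device effect will be made", and "this will include listings and tables by treatment, severity, relatedness and outcomes". No test or threshold is attached.

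**The concern.** Not knowing whether sequelae exist is different from knowing that there are none. The rule gives both states the same code, and it is the most favourable code on the list. Because the safety assessment is descriptive, a reader depends on the table labels meaning what they say. A row headed *Resolved*, read with its definition, looks like a count of confirmed full recoveries, but under the rule it may also contain events for which that was never established. The possible error runs in one direction only, towards more apparent complete recovery.

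**Working it through.** The plan gives no figure on this point, so there is none to reproduce. The check is a comparison of the categories, followed by a bound on the effect.

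**Step 1. Where each state is coded under section 8.2.5.**

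| State of the event | Code |
|---|---|
| Subsided, sequelae checked and absent | *Resolved* |
| Subsided, sequelae known to persist | *Resolved with sequelae* |
| Subsided, sequelae status not known | *Resolved*, by the added sentence |
| Not yet recovered | *Ongoing* |
| Current status not available | *Unknown* |

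The first and third rows share a code. *Resolved with sequelae* requires known persistence. *Unknown* requires that the current status itself is unavailable, which is not so for an event known to have subsided. No category as defined separates the third row from the first.

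**Step 2. Where the code is used.** Section 9.2 makes outcome one of the dimensions of the tables and listings for adverse device effects (ADEs), so the merged row enters the safety assessment. The endpoint in section 3.4.1 is occurrence: an ADE counts once whatever its outcome code. The counts that define the endpoint do not move.

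**Step 3. Bound on the effect.** The documents give neither of these quantities, so both are assumptions:

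- u = share of *Resolved* events with unknown sequelae status
- s = share of those events that truly have sequelae

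Overstatement of *confirmed* full recovery, as a share of *Resolved* events, is u. Overstatement of *true* full recovery is u × s.

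| u | s = 0 | s = 25% | s = 50% | s = 100% |
|---|---|---|---|---|
| 0 | 0 | 0 | 0 | 0 |
| 10% | 0 | 2.5% | 5% | 10% |
| 20% | 0 | 5% | 10% | 20% |
| 30% | 0 | 7.5% | 15% | 30% |

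The product is never negative and never exceeds u, so the *Resolved* row is an upper bound on confirmed full recovery.

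**Step 4. Illustration with assumed counts.** Take 20 ADEs on one surface: 14 confirmed free of sequelae, 2 with sequelae, 4 not established.

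- As coded: (14 + 4)/20 = 90% *Resolved*.
- Confirmed: 14/20 = 70%, with 4/20 = 20% unknown.
- True full recovery lies between 70% and 90%. If s = 25%, one of the four has sequelae and the true share is 17/20 = 85%, so the table is 5 points too high rather than 20.

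The 20-point gap is unconfirmed recovery. It is not a measured error.

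**The case against.** The strongest reply is that little rests on this code. The endpoint is occurrence, the assessment is descriptive with no recovery threshold, and the same rule applies to both surfaces. All of that stands. A reader might infer that the safety co-primary result is distorted or that one surface is favoured, but the documents support neither.

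A reader might also infer that lasting harms go under-counted. That does not follow. Table 5 lists permanent paresthesia, gingival recession, bone damage and excessive bone loss as event terms in their own right, and section 7.3.12 asks investigators to use those terms where applicable. Once found, such a consequence can be reported as its own event, whatever code an earlier infection or swelling carries. Nor does the rule sweep in a nerve symptom that has merely improved: that event has not recovered and fits *Ongoing*.

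Other provisions shrink the unknown group. Section 8.4 pursues outcomes until resolution or the last data queries. Table 2 schedules peri-apical X-rays at loading and at 12 months, probing at 12 months and photographs at every visit. The footnote to Table 5 has bone level changes above 1.5 mm between loading and 12 months flagged for review. Section 8.2.5 asks for every effort to establish the outcome of an ADE.

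These provisions reduce the problem but do not undo the coding rule. Follow-up under section 8.4 may stop once an event is resolved. Between loading and 12 months no X-ray or probing is scheduled, so an event that subsides in that interval can be coded without either check.

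**Conclusion.** The point holds as a minor reporting weakness. The rule places events with unknown sequelae status in the most favourable outcome row, no other category catches them, and that row feeds the descriptive safety tables. The tables *can* therefore overstate confirmed complete recovery. It would be tempting to say that they *do*, but that needs three things the documents do not show: that some subsided events have unknown sequelae status, that some of those truly have sequelae (for true recovery to be overstated), and that readers take *Resolved* as confirmed.

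The size cannot be determined from the documents. It is u × s of the *Resolved* events for true recovery and at most u for confirmed recovery, with both shares assumed. The occurrence endpoint is unchanged, and no between-surface bias is shown.

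**What to change.** Delete the second sentence of the *Resolved* definition in section 8.2.5 and reserve that code for events with sequelae confirmed absent. Add an eCRF outcome option for resolved events with sequelae status unknown, and show it as its own row, by surface, in the ADE outcome tables. Re-query events already coded *Resolved*, since section 3.6 puts the first enrolment in October 2019.

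If the eCRF can no longer be changed, state in the outcome tables that *Resolved* includes events with unknown sequelae status and is an upper bound on confirmed full recovery.

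The cost is one deleted sentence, one eCRF option, one table row and some re-querying of sites. The reported share of fully resolved ADEs may look less favourable. The fallback costs only a table note, but leaves the two groups inseparable.
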